#### **7.2.6.3.2. Mantoux/Purified Protein Derivative (PPD) Tuberculin Skin Test**

Mantoux Purified Protein Derivative (PPD) tuberculin skin test will be allowed during screening period, if there are two consecutive indeterminate results of QFT-G or T-SPOT test in subjects who have not received BCG vaccination. Subjects must have a Mantoux/PPD tuberculin skin test administered and then evaluated by a health care professional 48 to 72 hours later. If performed, a negative Mantoux/PPD tuberculin skin test result is required to meet the inclusion criterion.

The Tuberculin Test consists of intracutaneous injection of PPD in 0.1 mL of solution on the volar aspect of the forearm, using a short beveled 26-or 27-gauge needle (Mantoux test). The test is positive if the diameter of the erythema is over 10 mm in 48 to 72 hours after injection.

#### **7.2.6.4. Serum Lipid Profile**

Total cholesterol, LDL-cholesterol, HDL-cholesterol and triglycerides will be measured during the study requiring subjects to be fasting at least 9 hours prior to Visit 1, Visit 2, Visit 3 and Visit 5. Refer to [Appendix 10](#) for recommended clinical management of cholesterol.

#### **7.2.6.5. Creatinine Clearance**

A commonly used surrogate marker for actual creatinine clearance is the Cockcroft-Gault formula (refer to [Appendix 4](#)), which employs creatinine measurements and a subject's weight to predict the clearance. For subjects to be eligible for the study, GFR needs to be >40 mL/min based on Cockcroft-Gault calculation. Cockcroft-Gault GFR calculation will be done as part of clinical laboratory tests in Visit 1.

#### **7.2.7. Adjudicated Adverse Events**

Specific safety events such as cardiovascular (CV) events, malignancies, opportunistic infections (OI), hepatic events and interstitial lung disease (ILD) in this study will be adjudicated by external or internal committees to harmonize and to standardize selected safety event assessments (Refer to Section [9.6](#)).

Subjects will be monitored for development of any CV events, malignancies, infections (viral, bacterial, and fungal), liver disease and lung disease during the study.

The study site has responsibility to obtain and submit the event documentation to related committee. Event documentation will vary with the event requiring adjudication and may include (but not be limited to): hospital discharge summaries, operative reports, clinic notes, ECGs, diagnostic tests, pathology reports, autopsy reports and death certificate information, as applicable. Criteria for defining specific events will be provided to investigators in a separate study document.

Refer to [Appendix 11](#) for the steps to take in the event of potentially malignant tumors, lymphadenopathy or possible extra-nodal lymphoproliferative disorder (LPD) which might arise in the course of this study.

### **7.3. Banked Biospecimens**

#### **7.3.1. Markers of Drug Response**

Studying the variation in genetic markers and other biomarkers may help to explain some of the variability in response seen with some drugs among different individuals. This is referred to as pharmacogenomic/biomarker research. Comparing the deoxyribonucleic acid (DNA), ribonucleic acid (RNA), protein, and metabolite variation patterns of subjects who respond well and those who respond poorly to treatment may help to better define the most appropriate group of patients in which to target a given treatment. Collecting biospecimens for exploratory pharmacogenomic/biomarker analyses and retaining them in the Pfizer BioBank makes it possible to better understand the drug's mechanism of action and to seek explanations for differences in, for example, exposure, efficacy, tolerability, or safety not anticipated prior to the beginning of the study. Providing these biospecimens is a required study activity for study sites and subjects, unless prohibited as such by local regulations or ethics committee (EC) decision.

To protect subjects' confidentiality, the banked biospecimens and data generated from them will be coded with the subject's study identification (ID) number. Samples will be kept in a facility accessible only by badge-swipe. Data will be stored on password-protected computer systems. The key between the code and the subject's personal identifiers will be held at the study site; the researchers using the biospecimens and data generated from them will not have access to the key nor any personally identifying information. Biospecimens will only be used for the purposes described here and in the informed consent document/patient information sheet; any other uses require additional ethical approval. Unless a time limitation is required by local regulations or ethical requirements, biospecimens will be stored indefinitely to allow for future research on the topics described here, including research conducted during the lengthy drug development process and also postmarketing research. Subjects can withdraw their consent for the use of their biospecimens at any time by making a request to the investigator, in which event any remaining biospecimen will be destroyed; data already generated from the biospecimens will continue to be stored to protect the integrity of existing analyses. It is very unlikely that results generated from the biospecimens will have any clinical, diagnostic, or therapeutic implications for the individual study participants. Subjects are notified in the informed consent document/patient information sheet that their results will not be given to them, unless required by local laws or regulations, in which case results will be returned via the investigator. Results will not be provided to family members or other physicians, nor will they be recorded in the subject's medical record. There is no intention to contact subjects after completion of the clinical study.

A 4 mL blood biospecimen, **Prep D1 (K2 edetic acid (ethylenediaminetetraacetic acid) (EDTA) whole blood collection optimized for DNA analysis)**, will be collected at the baseline visit to be retained for potential pharmacogenomic/biomarker analyses related to drug response, unless prohibited by local regulations or EC decision. For example, putative safety biomarkers, drug-metabolizing enzyme genes, drug-transport protein genes, or genes thought to be related to the mechanism of drug action may be examined.

The Banked Biospecimens will be collected from all subjects **unless prohibited by local regulations or ethics committee decision**. Detailed collection, processing, storage and shipment instructions are provided in the central laboratory manual.

It is possible that the use of these biospecimens may result in commercially viable products. Subjects will be advised in the informed consent document/patient information sheet that they will not be compensated in this event.

### 7.3.2. Additional Research

Unless prohibited by local regulations or ethics committee decision, subjects will be asked to indicate on the consent form whether they will allow the banked biospecimens to also be used for the following research:

- Investigations of the disease under study in the clinical study, and related conditions;
- Biospecimens may be used as controls. This includes use in case-control studies of diseases for which Pfizer is researching drug therapies; use in characterizing the

natural variation amongst people in genes, RNA, proteins, and metabolites; and use in developing new technologies related to pharmacogenomics/biomarkers.

Subjects need not provide additional biospecimens for the uses described in this section; the biospecimen specified in the Markers of Drug Response section will be used. Subjects may still participate in the clinical study if they elect not to allow their banked biospecimens to be used for the additional purposes described in this section.

#### 7.4. Assessment of Suicidal Ideation and Behavior (SIB)

There are no current medically significant suicidality concerns for the study drug (ie, tofacitinib) in this study or their respective mechanisms of action. Ongoing and aggregate cumulative safety reviews and pharmacovigilance activities will be conducted; if any concerns are identified that would warrant changes to these assessments, surveillance tools will be implemented, as appropriate.

#### 7.5. Triggered Requirements

The following laboratory abnormalities require re-testing ideally within 3-5 days, prompt retesting, withdrawal of study treatment or withdrawal from this study.

Condition	Action
Neutrophil counts <1000 cells/mm 	The subject should return to the study site for prompt retesting, ideally within 3-5 days.
Platelet counts <100,000 platelets/mm 	The subject should return to the study site for prompt retesting, ideally within 3-5 days.
Lymphocyte counts <500 lymphocytes/mm 	The subject should return to the study site for prompt retesting, ideally within 3-5 days.
Any single AST and/or ALT elevation $\geq 3 \times$ ULN *	The subject should return to the study site for prompt retesting, ideally within 3-5 days.
Any single hemoglobin value <8.0 g/dL or one that drops $\geq 2$ gm/dL below baseline.	The subject should return to the study site for prompt retesting, ideally within 3-5 days.
Any serum creatinine increase >50% over the average of screening (most recent value prior to baseline) and baseline values OR an absolute increase in serum creatinine >0.5 mg/dL (>44.2 $\mu$ mol/L) over the average of screening (most recent value prior to baseline) and baseline values	The subject should return to the study site for prompt retesting, ideally within 3-5 days.

* The subject must return to the study site for prompt retesting and include the following tests: albumin, creatine kinase (CK), total bilirubin, direct and indirect bilirubin, GGT, PT/INR, and ALP. Additional investigations include a detailed history, occupational exposure, sexual history, travel history, history of contact with a jaundiced subject, surgery, blood transfusion, history of liver or allergic disease, work exposure, history of ethanol, recreational drug and dietary supplement consumption. Testing for acute hepatitis A, B or C infection and biliary tract imaging may be considered.
	

Condition	Action
2 sequential AST or ALT elevations $\geq 3 \times$ ULN with a total bilirubin value $\geq 2 \times$ ULN	Treatment with all study drugs will be discontinued and the subject withdrawn from this study. Follow-up to resolution
2 sequential AST or ALT elevations $\geq 3 \times$ ULN with an elevated INR	Treatment with all study drugs will be discontinued and the subject withdrawn from this study. Follow-up to resolution
2 sequential AST or ALT elevations $\geq 3 \times$ ULN accompanied by symptoms consistent with hepatic injury	Treatment with all study drugs will be discontinued and the subject withdrawn from this study. Follow-up to resolution
2 sequential AST or ALT elevations $\geq 5 \times$ ULN, regardless of Total Bilirubin or accompanying symptoms	Treatment with all study drugs will be discontinued and the subject withdrawn from this study. Follow-up to resolution
2 sequential hemoglobins $< 8.0$ g/dL or a decrease of more than 30% from baseline value	Treatment with all study drugs will be discontinued and the subject withdrawn from this study. Follow-up to resolution
2 sequential platelet counts $< 75,000$ platelets/mm 	Treatment with all study drugs will be discontinued and the subject withdrawn from this study. Follow-up to resolution
2 sequential neutrophil counts $< 1000$ cells/mm 	Treatment with all study drugs will be discontinued and the subject withdrawn from this study. Follow-up to resolution
2 sequential lymphocyte counts $< 500$ lymphocytes/mm 	Treatment with all study drugs will be discontinued and the subject withdrawn from this study. Follow-up to resolution
Confirmed increases in serum creatinine $> 50\%$ over the average of screening and baseline values.	Treatment with all study drugs will be discontinued and the subject withdrawn from this study. Retesting should occur until the serum creatinine is within 10% of the pretreatment value.
Serious infections defined as any infection (viral, bacterial, or fungal) requiring parenteral antimicrobial therapy or hospitalization for treatment, or meeting other criteria that require the infection to be classified as a serious adverse event.	Treatment with all study drugs will be discontinued and the subject withdrawn from this study.
Opportunistic infection judged significant by investigator	Treatment with all study drugs will be discontinued and the subject withdrawn from this study.
Malignancies excluding adequately treated non- melanoma skin cancer (NMSC) and cervical carcinoma in situ	Treatment with all study drugs will be discontinued and the subject withdrawn from this study.

Condition	Action
Increase lipid parameters (total cholesterol, LDL cholesterol, HDL cholesterol, triglycerides)	Monitor and treat according to local guidance (eg, diet and behavior modification, statin therapy).
Pregnancy or refusal to use appropriate contraception	Permanently withdraw the subject from the study drug and follow any pregnancy to resolution.
Anaphylactic or other serious allergic reaction	Immediately discontinue study drug and institute appropriate therapy.
Symptoms suggestive of a lupus-like syndrome	Discontinue study drug and institute appropriate therapy.
Detection of HBV-DNA by the two sequential quantitative tests (for subjects who have HBV-DNA assay at screening)	Immediately discontinue study drug and institute appropriate therapy.
Other serious or severe AEs, after consultation with the sponsor.	Treatment with all study drugs will be discontinued and the subject withdrawn from this study.
ALT = alanine aminotransferase; AST = aspartate aminotransferase; ALP = alkaline phosphatase; DNA = deoxyribonucleic acid; g/dL = grams per deciliter; GGT = gamma-glutamyl transferase; HBV = hepatitis B virus; PT/INR = Prothrombin Time/International Normalized Ratio; mm = millimeter; × ULN = times the upper limit of normal	

Additional individual subject safety monitoring in above actions is at the discretion of the investigator and dependent on any perceived safety concerns. Unscheduled laboratory testing through the central laboratory may be obtained at any time during the study to assess such concerns, and a subject may be withdrawn at any time at the discretion of the investigator.

Because of the potential higher risk of interstitial pneumonia in Japanese patients than in Western patients, investigators should carefully evaluate all patients who exhibit symptoms, especially fever and cough.

If a patient develops fever, cough, or dyspnea, temporary discontinuation of study drug should be considered. The differential diagnosis should include assessment for pneumonia, TB, pneumocystis pneumonia (PCP), and invasive fungal infection.

Additionally, if a patient's absolute lymphocyte count is decreased to  $<1000/\text{mm}^3$ , please consider appropriate action based on the patient's condition, such as retest of lymphocyte counts, as warranted. If the absolute lymphocyte count is decreased to  $<500/\text{mm}^3$ , prompt retesting, ideally within 3-5 days from the awareness, is required and please consider temporary discontinuation of study drug while the patient is under evaluation for the cause of the abnormality (ies), e.g., pneumonia, TB or PCP.

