## 6.2. Study Period

Eligible subjects will be randomized and treated in a double-blind fashion. Refer to [SCHEDULE OF ACTIVITIES](#) for the detail overview of the procedures.

Subjects who discontinue assigned investigational drug are required to continue in the study and perform all study tests and procedures until the study is complete.

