### **6.4. Subject Withdrawal**

Subjects may withdraw from the study at any time at their own request, or they may be withdrawn at any time at the discretion of the investigator or sponsor for safety or behavioral reasons, or the inability of the subject to comply with the protocol required schedule of study visits or procedures at a given study site.

If subjects withdraw prior to Week 12 (Visit 5), the subject should complete the procedures for Week 12 (Visit 5) (refer to section 6.2.4).

It is important to continue all subjects in the study and perform all tests and procedures until the study is completed to enable collection of safety data, even if a subject withdraws from the study assigned treatment, unless the subject withdraws their consent to continue participation.

If a subject does not return for a scheduled visit, every effort should be made to contact the subject and document their current status. All attempts to contact the subject and information received during contact attempts must be documented in the subject's medical record. In any circumstance, every effort should be made to document subject outcome, if possible. The investigator should inquire about the reason for withdrawal, request the subject to return all unused investigational products, request the subject to return for a final visit, if applicable, and follow up with the subject regarding any unresolved Adverse Events (AEs).

If the subject withdraws from the study, and also withdraws consent for disclosure of future information, no further evaluations should be performed, and no additional data should be collected. The sponsor may retain and continue to use any data collected before such withdrawal of consent.

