## **8.2. Reporting Period**

For SAEs, the active reporting period to Pfizer or its designated representative begins from the time that the subject provides informed consent, which is obtained prior to the subject's participation in the study, ie, prior to undergoing any study-related procedure and/or receiving investigational product, through and including 28 calendar days after the last administration of the investigational product. SAEs occurring to a subject after the active reporting period has ended should be reported to the sponsor if the investigator becomes aware of them; at a minimum, all SAEs that the investigator believes have at least a reasonable possibility of being related to study drug are to be reported to the sponsor.

AEs (serious and nonserious) should be recorded on the Case Report Form (CRF) from the time the subject has taken at least 1 dose of study treatment through the subject's last visit.

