##### **8.5.2. Serious Infections**

A serious infection is any treated infection that requires hospitalization for treatment or requires parenteral antimicrobial therapy or meets other criteria that require it to be classified as a serious adverse event. A patient who experiences a serious infection should be discontinued from the study and the serious adverse event should be listed as the reason for discontinuation in the eCRF. Appropriate laboratory investigations, including but not limited to cultures should be performed to establish the etiology of any serious infection. All adverse events, including serious adverse events, should be reported as described in Section 8.2 on Adverse Event Reporting.

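### Protocol 7.5 and 8.5.2 withdraw subjects from the study where 6.2 and 6.4 keep them in after drug stop, so recording of new adverse events up to Day 85 can differ by site

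*Protocol*

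**What the plan says.** Protocol 6.2 sets the rule for subjects off drug: "Subjects who discontinue assigned investigational drug are required to continue in the study and perform all study tests and procedures". It names no exception. Protocol 6.4 gives the reason, which is safety data: "It is important to continue all subjects in the study and perform all tests and procedures until the study is completed". The only exception in that sentence is withdrawn consent. The same section also allows discretionary withdrawal, saying of subjects that "they may be withdrawn at any time at the discretion of the investigator or sponsor for safety or behavioral reasons", and asks anyone who withdraws early to complete the Visit 5 procedures.

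The table in Protocol 7.5 goes the other way. In 13 rows the action is: "Treatment with all study drugs will be discontinued and the subject withdrawn from this study". Section 8.5.2 adds: "A patient who experiences a serious infection should be discontinued from the study". The wording of 7.5 does not look loose. Its lead-in lists "withdrawal of study treatment or withdrawal from this study" as separate actions, and some rows stop drug only, for example "Permanently withdraw the subject from the study drug and follow any pregnancy to resolution".

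Under Protocol 8.2, serious and non-serious AEs go on the CRF from "the time the subject has taken at least 1 dose of study treatment through the subject's last visit". Active reporting of serious AEs (SAEs) runs to 28 days after the last dose. Section 6.3 plans no follow-up visit but allows one at the investigator's discretion.

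**The concern.** The same subject is covered by two opposite instructions. Neither 7.5 nor 8.5.2 refers to 6.2 or 6.4, or the reverse, and no sentence sets an order of precedence. One site can take the 13 rows literally and end participation; another can take the requirement in 6.2 literally and keep the subject to Week 12.

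At stake is the completeness of the safety comparison, which is a secondary objective. The affected subjects have just had a serious infection, an opportunistic infection, a malignancy, another serious or severe event, or a confirmed laboratory abnormality. Section 1.2 names serious infection and malignancy among the important risks. These are the subjects for whom 6.4 wants data collection to go on.

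**Working it through.** The plan gives no figure on this point, so there is none to reproduce. The check is a row count and date arithmetic.

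**Rows of Protocol 7.5 that stop drug**

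- Stop drug and withdraw from the study: 4 liver rows, 4 haematology rows (haemoglobin, platelets, neutrophils, lymphocytes), creatinine, serious infection, opportunistic infection, malignancy, and other serious or severe AEs. That is 4 + 4 + 1 + 4 = 13.
- Stop drug only: pregnancy or refusal of contraception, serious allergic reaction, lupus-like syndrome, HBV-DNA detection. That is 4.
- Total: 13 + 4 = 17.

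Of the 13, 8 order follow-up until resolution, 1 (creatinine) orders retesting, and 4 state no follow-up in the row.

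**Days without CRF recording of new AEs**

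Inputs: planned Visit 5 on Day 85 (6.2.4); CRF recording to the last visit and active SAE reporting to 28 days after the last dose (8.2). Assumptions: last dose and early termination visit both on Day D, and no later visit.

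- Under 7.5, days lost = 85 − D. Under 6.2, days lost = 0.
- Days lost that are also outside active SAE reporting = max(0, 85 − (D + 28)).

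| Stop day D | Days lost under 7.5 | Covered by active SAE reporting | Not covered |
|---|---|---|---|
| 15 | 70 | 28 | 42 |
| 29 | 56 | 28 | 28 |
| 43 | 42 | 28 | 14 |
| 57 | 28 | 28 | 0 |

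Visit 5 may fall 3 days either side of Day 85, so the Day 29 figure ranges from 82 − 29 = 53 to 88 − 29 = 59.

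**Laboratory rows.** Scheduled post-baseline chemistry and haematology are at Visits 3 and 5 only (Table 5). Apart from unscheduled tests, these rows therefore matter around Week 4. With Visit 3 on Days 26 to 32 and a retest 3 to 5 days later, the stop falls on Days 29 to 37. The loss to Day 85 is then 48 to 56 days, or up to 59 with Visit 5 on Day 88, and it is shorter if ordered follow-up brings later visits.

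**Primary analysis.** SAP Appendix 1 drops data collected more than 7 days off drug, and Visit 4 has no efficacy assessment. For a stop before Day 72, neither rule gives a Week 12 value: the termination visit falls before the Week 12 window, and Visit 5 is at least 82 − 71 = 11 days off drug. With Visit 5 on Day 85, the rules differ at Week 12 only for stops on Days 72 to 77, where a termination visit counts but Visit 5 is 8 to 13 days off drug. An early termination visit can also supply a Week 4 value that 6.2 would not. Both effects are confined to a few possible subjects.

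**The case against.** The best defence is that the sections can be reconciled. Section 6.4 permits safety withdrawal, and 7.5 keeps drug-only rows apart from study-withdrawal rows, so the 13 rows can be read as safety withdrawals fixed in advance, with 6.2 governing everyone else. That is a fair reading, but it is not stated. The withdrawal in 6.4 is discretionary, and the 13 rows are not framed as discretion. Even if this reading were adopted, it would end the data collection that 6.4 asks for.

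The case for a small impact largely stands:

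- After a stop, what is lost is new, mainly non-serious events off drug. Section 8.4.1 expects more than 95% of a dose to be eliminated within 24 hours.
- SAE reporting rules are the same under both readings, and later SAEs are still reported if the investigator learns of them.
- Whether late events enter the AE tables depends on sponsor data standards that are not in these documents.

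A reader might infer that the four clinical rows leave subjects with no follow-up. The documents do not support that: 6.4 provides for following unresolved events, 8.1 requires the outcome of every AE to be pursued, and the text after the 7.5 table allows further monitoring for any row. These provisions mainly concern existing events, but so does the follow-up ordered in the laboratory rows. The contrast between the 4 rows and the other 9 is one of degree.

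A reader might also infer that responder rates are at risk. That needs two assumptions: that dropout in SAP Section 7 means leaving the study, and that the carry-forward of components applies when a whole visit is excluded. Even then, one Week 4 responder moves an arm by up to 1/100 = 1 point. The confidence interval half-width is 1.96 × √(2p(1 − p)/100), which is 13.9 points at p = 0.5 and 12.7 at p = 0.7 (assumed response rates). Protocol 9.2.5 makes these comparisons descriptive.

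**Conclusion.** The conflict holds: 13 of 17 drug-stop rows, plus 8.5.2, contradict 6.2 and the continuation sentence of 6.4, and no precedence is given. The consequence is uneven recording of new, mainly non-serious AEs between drug stop and Day 85. For a Day 29 stop the loss is up to 56 days to Day 85, with 28 covered by active SAE reporting. That rests on a same-day termination visit and no later visit; any follow-up visit shortens it.

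The documents give no trigger rates, so the number of subjects cannot be estimated and no effect on the AE comparison can be computed. The non-inferiority conclusion is not in question. Importance is minor to moderate.

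**What to change.** In the 13 rows of Protocol 7.5 and in 8.5.2, replace withdrawal from the study with: *discontinue study drug; continue scheduled visits and safety assessments per 6.2 unless consent is withdrawn*. Keep every stopping threshold, the follow-up and retesting text, and the discretion to withdraw in 6.4.

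The cost is a wording amendment, plus attendance by a few off-drug subjects at the remaining Week 8 and Week 12 visits. Visit 4 involves mainly AE and medication review; Visit 5 adds examination, laboratory tests and questionnaires. For a stop on Days 72 to 77 with Visit 5 on Day 85, the Week 12 efficacy value would fall outside the 7-day rule, a small loss.

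Optionally, define dropout for the binary endpoints in SAP Section 7 as permanent discontinuation of study drug, so that non-responder imputation does not depend on which rule a site followed. Resolving the conflict needs no change to the concomitant-treatment rules in 5.8 and no extra set of Visit 5 procedures at drug stop.
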